3.1. Primary endpoints

The **primary objective** of the assessment study is to compare the acceptance and the performance of the AIDAVA prototype versus existing practice, and between the 2 versions of the prototype. To this end, we propose to measure the following endpoints that will be recorded across sites.

Objective	Primary Endpoints
Metric 1. Evaluate acceptance by end users	Metric definition: Structured questionnaire (adapted from a System Usability Scale with additional questions such as I would recommend AIDAVA to my friend, colleague, or family member I am interested / ready to work with AIDAVA when available on the market I understand the purpose of data curation I am ready to spend the needed time to ensure proper data curation The curation process was perfect/acceptable/too long for me Measurement score (M1) through structured questionnaire (System Usability Scale - form) provided in REDCap
Metric 2. Measure	Metric definition
impact on workload for quality enhancement of data (including quality of the different curation tools)	 Compare time spent in curating data in G0 (current situation) G1 (generation 1 of the prototype) G2 (generation 2 of the prototype). Check the amount of data curated in the average time: are there more data being curated together with the ones needed to support the use case
	 Measurement For estimated time spent in curating (M2.1) User entry in dedicated "Curator form" (RedCap) For curators, when requesting an estimate for G0, it is important to ensure that curated data set have the same level of complexity as for G1 and G2 complexity: Extract a sample (synthetic data ?) to be curated including several data sources; Request existing registry stewards to provide a time to curate data up to insertion into registry (M2.2) System check "active" time of user to answer a query Amount of additional data elements are curated automatically computed (M2.3) How many data elements have been curated automatically by the systems (M2.4) How many data elements have required human interventions and been successful answered by the patients (i.e. answer provided to the question)

Objective	Primary Endpoints
	 (M2.5) How many data elements have required human interventions can not be answered by the patients and are sent to the curators (M2.6) How many data elements send to the curators did not get appropriate answer to finish the curation process

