4.1 Overall Design

The assessment study will be a cohort, 3 arms, prospective¹³ study involving 30 patients (15 breast cancer and 15 CVD) + 3 expert curators in each site. It will be based essentially on available data, collected during clinical care (see Section 10.1 for detailed description of data sources), but will also include some prospective data from medical devices and Quality of Life questionnaire

There will be 3 arms that will allow comparison across these different populations of users.

- "G1 and G2" patients who contributed to evaluation of G1 and G2.
- "Single Generation" patients who contribute to the evaluation of only one generation of the prototype (G1 or G2)
- Expert data curators

There will be 4 epochs

- Epoch 1 will last 1 week and take place just before deployment and evaluation of G1; it will allow to gather information from the expert curator on the current situation/curation process and to provide a dedicated training to the curators.
- Epoch 2 will last for 2 weeks, and is expected to take place in the period of July September 2024. Patients will be requested to ingest their data with the support of the prototype, and to curate them. Whenever needed, the data expert curator will be able to support them.
- Epoch 3 will last for 16 to 18 months: "wash out" period during which G2 of the prototype will be developed;
- Epoch 4 will last for 2 weeks and is expected to take place in the period February/March 26. Patients and curators will be requested to assess Generation 2 (G2) of the prototype, by performing the same task as in Epoch 2 to enable comparison of the performance of the 2 generations of the prototype.

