4.4.4. Returning patients (for G2 only)

This is applicable only for patients who have participated to the assessment of G1 and are also assessing G2

	CVD patients	BC patients
2 weeks for start G2: Jan 2026	Refresh training of Expert curators and Research associates	
G2 VISIT 1 - on site W1 Day 1	 Upload of all data (starting from scratch) Patient will be called in for outpatient visit by the res Questionnaire to specify user profile (In Redcap, Use Training session for the patient on the prototype - G Patient fills EQ-5D QALY - quality of life questionnaire Research associate complete REDCap Form (in REDC Patient and expert curator curate medical data with 	search associate er Profile FORM) 2 version - by the research associate (2,5h) e through HDI provided app ap, Patient monitoring FORM) for enrolled patients AIDAVA
W1 Day 2-5	 CVD patient use the medical device Patient will use AIDAVA and test its functionalities, ta Expert Curator will curate the data in AIDAVA, on der RA fill the patient monitoring form (in REDCap, Patient) 	ake notes and if necessary, will contact helpdesk mand ent monitoring FORM)

	CVD patients	BC patients
W1 Day 5	 First calculation of SMART risk score by AIDAVA (automatically) and CVD expert (manually). Data collection and entry forms documentation of SMART risk score calculation result and time (in REDCap, Patient monitoring FORM) 	 System extracts the patient data for insertion into the local AIDAVA BC registry Queries identified as secondary end points will be fired automatically by the system and results available for display to the BC data users
	 AIDAVA extract IPS and forward it automatically to th Data curators spreadsheet (Patient as curator and E Form) Data user/consumers spreadsheet (In REDCap, Data 	ne HDI (+ enter flag in REDCap, Patient monitoring Form) Expert Curator). (in REDCap, Patient Curator FORM; Expert Data Curator user/consumer Form)
VISIT 2 - online W2 Day 1	CVD patients use medical device Check if there is any issue with the medical device (CVD patient only)	
	 Second training session on the prototype - online (open questions) Patient and expert curator curate medical data using AIDAVA RA fill the patient monitoring form (in REDCap, Patient monitoring Form) 	
W2	CVD patient use the medical device	

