9.2 Analysis Sets

Primary endpoint components

The analysis set will include all expert curators and patient participants and will take into account the primary data points (PDP) identified in yellow in the figure below across the 3 arms.

Primary Data Point	Generation	Arm	Description of measures (through RedCap Form and computed)		
PDP1	G0		M2.1 : Estimated time spent in curation per patient record (min)		
PDP2	G1	Expert Curator	M1: System Usability Score M2.1: Estimated time spent in curation per patient record (min)		
PDP3	G2		Same than for G1 - measured for G2		
PDP4	G1	G1 AND G2 users	 M1: System Usability Score M2: Time spent in for curation in min Estimated time in RedCap form (M2.1) Computed "active" time to answer queries (M2.2) Computed amount of data elements curated automatically by system (M2.3) requiring human intervention with answer from the patient (M2.4) 		

Primary Data Point	Generation	Arm	Description of measures (through RedCap Form and computed)
			 without answer the patient and requiring curator input (M2.5) without answer requested from curator but not successful (M2.6)
			M3: Computed data quality scores of curated record in terms of completeness, correctness, consistency and trustworthiness (as detailed in Task 4.6).
			 M4: Computed quality of the NLP concept extraction against the manually annotated data ("gold standard") Precision (M4.1) which measures the fraction of gold standard instances among the retrieved instances Recall (M4.2) which measures the fraction of the gold standard concepts that could successfully be retrieved
PDP5	G2		Same than PDP4 - for G2
PDP6	G1	G1 OR G2	Same than PDP4 - for G1
PDP7	G2	users	Same than PDP5 - for G2

Secondary endpoints

The analysis set will include all data users (BC specialists and CVD experts) and will take into account the secondary data points (SDP) identified in orange in the figure below across the patient arms. As indeed this is about reuse of data, after the curation process; there is no effect expected from the fact that patients did use G1 before G2 or not.

Secondary Data Point	Generation	Arm	Description of measures (through RedCap Form and computed)		
			Breast Cancer		

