9.3 Statistical Analyses

Three tests have be retained

- **Paired t-test**: statistical test that compares the means of two related groups, where each subject is measured at two different time points or under two different conditions. It is used to determine if there is a significant difference between the two groups.
- Mann-Whitney U test (unpaired t-test): non-parametric statistical test used to compare the medians of two independent groups. It is often used when the data are not normally distributed or when the sample sizes are small.
- Wilcoxon signed-rank test: non-parametric statistical hypothesis test used to compare two populations with two matched samples.

Primary Endpoint(s) Analysis

The endpoints are defined in Section 9.2 will be used to support the analysis

Computed	Description of measures	Test & meaning (per H1)			
	Population: Expert Curators				
E1	Difference between data points 1 and 2: E1.M2.1△ = M2.1@PDP1 - M2.1@PDP2 E1.M2.2△ = M2.2@PDP1 - M2.2@PDP2	Paired t-test H1: less time spent in curation in G1 than in G0 for expert curators			
E2	Difference between data points 2 and 3: E2.M1-Δ = M1@PDP2 - M1@PDP3	Paired t-test H1: G2 is more usable than G1 for expert curators			
	E2.M2.1∆ = M2.1@PDP2 - M2.1@PDP3 E2.M2.2∆ = M2.2@PDP2 - M2.2@PDP3	H1: less time spent in curation in G2 than in G1 for expert curators			
	Population:	Patients			
P1	Difference in data points 4 and 5 (i.e. difference between G1 and G2 for arm where patients used G1 AND G2)	Paired t-test (effect of system + training/experience from G1)			
	P1.M1- = M1@PDP4 - M1@PDP5	H1: G2 more usable than G1			
	P1.M2.x∆ = M2.x@PDP4 - M2.x@PDP5	H1: G2 requires less time for curation than G1 H1: G2 enables curation with less human intervention than G1			
	P1.M3-∆ = M3@PDP4 - M3@PDP5	H1: G2 provide same or higher quality than G1			
P2	Difference in data points 6 and 7 (i.e. difference between G1 and G2 for arm where patients used G1 OR G2)	Unpaired t-test (effect of system only)			
	P2.M1- = M1@PDP6 - M1@PDP7	H1: G2 more usable than G1			
	P2.M2.x∆ = M2.x@PDP6 - M2.x@PDP7	H1: G2 requires less time for curation than G1 H1: G2 enable curation with less human intervention than G1			
	Ρ2.Μ3-Δ = M3@PDP6 - M3@PDP7	H1: G2 provide same or higher quality than G1			

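### P1 compares G1 and G2 curation effort as raw counts and minutes on a record that is 16-18 months longer at G2, so record growth can mask or reverse a real improvement

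*Protocol*

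**What the plan says.** Section 3.1 defines the components of Metric 2 as numbers of elements. M2.4, for example, is "How many data elements have required human interventions and been successful answered by the patients". M2.5 and M2.6 follow the same pattern for elements passed to the curators and elements the curators could not resolve. Section 9.2 lists M2.3 as "Computed amount of data elements curated automatically by system (M2.3" and introduces the patient time measure as "M2: Time spent in for curation in min".

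Section 9.3 then fixes the contrasts. P1 (patients who used both generations, paired t-test) is "M2.x@PDP4 - M2.x@PDP5", with the hypothesis "H1: G2 enables curation with less human intervention than G1". P2 (patients who used one generation, unpaired test) is "M2.x@PDP6 - M2.x@PDP7". A3 subtracts the pooled patient arms, and A4 subtracts P2 from P1 to isolate experience. Section 9.1 names M2 as one of the two critical metrics.

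On the G2 workload, Section 4.1 says the prototype is assessed "by performing the same task as in Epoch 2 to enable comparison of the performance of the 2 generations". For returning patients, Section 4.4.4 opens the first G2 visit with "Upload of all data (starting from scratch". Section 4.1 puts 16 to 18 months between the generations, and Annex 4 (Section 3.2) has data transferred afresh at the start of testing of each generation.

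**The concern.** The task is the same at G2 but the data set is not. A returning patient's G2 record contains what was available at G1 plus everything added since. For a CVD patient whose G1 visit fell during the index infarction stay, that includes the whole post-infarction follow-up from the sources in Section 10.1 (progress notes, laboratory and imaging reports, GP record). With raw differences, a longer record tends to raise M2.4, M2.5, M2.6 and the minutes, which counts against G2. It also raises M2.3, which counts for G2.

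The sign of a contrast on a critical primary metric could then reflect record growth instead of the tool. In A4 the growth is present in P1 but not shown in P2, so it need not cancel and could be read as a negative effect of experience.

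**Working it through.** **1. Is M2.1 a raw total?** The example patient form in Section 10.3.3 has 14 daily entries for ingestion and curation: 2:15, 3:00, 5:45, 5:30, 1:10, 2:05, 1:00, 3:30, 4:00, 1:00, 3:15, 2:20, 3:10 and 1:10. They sum to 2,350 minutes, which is the figure in the linked table. The entries for other activities sum to 840, also as shown. Nothing is divided by elements or record size.

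**2. Break-even growth.** Let N be the element count at G1, g the growth to G2, and h1 and h2 the shares needing a human. The counts are N·h1 and N·(1+g)·h2. With h2 = h1·(1-r), the G2 count is higher when (1+g)(1-r) > 1, that is g > r/(1-r).

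| Relative reduction r | Break-even growth |
|---|---|
| 5% | 5.3% |
| 10% | 11.1% |
| 20% | 25% |
| 30% | 42.9% |

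Reading r as tool improvement assumes that new elements need a human as often as old ones. The same algebra applies to minutes if time is proportional to elements.

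**3. Example** (assumed: 1,000 elements at G1, share falling from 30% to 25%). The share difference is 5 points in G2's favour at any growth. The raw difference G1 minus G2 is:
- 0% growth: 300 - 250 = +50
- 10%: 300 - 275 = +25
- 20%: 300 - 300 = 0
- 30%: 300 - 325 = -25
- 50%: 300 - 375 = -75

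Meanwhile M2.3 rises from 700 to 750 with no growth and to 1,125 at 50% growth.

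**4. Plausible growth.** The protocol gives no record sizes. If data accrue at a constant rate (an assumption), growth is (16 to 18 months)/12 divided by record length in years:

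| Record at G1 | Growth | Relative reduction G2 needs to break even |
|---|---|---|
| 2 years | 67-75% | 40-43% |
| 5 years | 27-30% | 21-23% |
| 10 years | 13-15% | 12-13% |
| 20 years | 7-8% | 6-7% |

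**5. Effect on the test.** In a simulation with assumed inputs (60 pairs, true share 30% to 25%, SD 8 points, record sizes log-normal), the paired t-test on shares favoured G2 in 91-92% of runs at every growth. On raw counts it favoured G2 in 84% of runs with no growth, 16% at 13% growth, and about 0% at 30% and 50%. It declared G2 significantly worse in 22% of runs at 30% growth and 90% at 50%.

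**6. Can a share mislead too?** Yes. Take 200 elements at G1 with 40 needing a human: 20%. Section 6.2 asks for three readings on one day a month after the evaluation, so 3 × 16 to 3 × 18 = 48 to 54 home blood pressure values. If 54 are added and all are curated automatically, the share becomes 40/254 = 15.7% with no change in the tool. The denominator therefore has to be protected.

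**The case against.** The best counter-argument is that the protocol already separates effort from volume. The synopsis limits the time endpoint to needed data elements and lists additional data as its own item. Section 3.1 asks separately how much data was curated, and M3 scores volume. This has some force, but the needed-elements wording covers time only. It does not appear in Section 9.2, in the forms or in the Section 9.3 contrasts, and volume is never used as a divisor. The equal-complexity requirement in Section 3.1 concerns the G0 estimate and sets no matching of G1 and G2 records.

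Other objections stand and limit the point:
- A reader might infer that every G1-G2 contrast compares against a longer record. P2 does not support that: it compares different first-time patients, who have no washout data. Only record size is unmatched there.
- A reader might take the washout blood pressure readings as proof of more human work. They come from a connected device, concern CVD patients only and may be curated automatically, so they are weak evidence of that.
- G2's language tools are hypothesised to have higher recall, which adds elements, but also higher precision, which removes spurious ones. The net effect on human work is unknown.
- Section 10.1 notes that GP records typically span a lifetime. With long records, growth is small and a moderate improvement would still show.

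**Conclusion.** The point holds for P1, and through it for A3 and A4. As fixed in Section 9.3, these contrasts confound tool performance with record growth on a critical metric. Growth can offset or reverse a real fall in M2.4 to M2.6, M2.1 and M2.2, and it inflates M2.3 in G2's favour. Reversal of the human-intervention count needs growth above r/(1-r): 11% for a 10% reduction in the share, 25% for a 20% reduction.

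It would be too strong to conclude that G2 will look worse, or that the bias always runs against G2. The record sizes, growth rates and shares used above are assumptions, and the direction differs by component. Because the protocol itself writes out the raw-difference formulas, this is not a detail merely left open for a later analysis plan. It should be corrected before the G2 comparison.

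**What to change.** In Section 9.3, replace the raw human-intervention differences by per-patient shares: (M2.4+M2.5)/(M2.3+M2.4+M2.5) for elements needing a human, and M2.6/M2.5 for those left unresolved. Compute them on the fixed set of needed elements the protocol already lists: the breast cancer registry list in Section 10.5 and the SMART inputs in Section 3.2.2. At the least, exclude home blood pressure device readings from the denominator, so that G2 gains no credit merely for emitting more elements. Report minutes both raw and per curated element, and keep the raw counts as description. For P2, state that record size is unmatched.

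The shares use counts the study already collects. The cost is a little extra analysis and tagging elements by type. If shares are taken over all elements, they still depend partly on how many elements the tool extracts, and so do minutes per element; this is why raw values should stay in the report.

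A sensitivity check in P1 restricted to elements dated before the patient's G1 cut-off is optional. It needs dated element-level output and cannot be applied to M2.1, because self-reported minutes cannot be split by element date.

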patients - across sites - receiving nodal radiotherapy out of any radiotherapy	P1 = Total number of patients 404684003 Clinical finding (finding) WITH 108290001 Radiotherapy (procedure)
	P2 = Total number of patients 404684003 Clinical finding (finding) WITH 168522007 Radiotherapy for lymphatic irradiation (procedure)

The actual metrics/ endpoints can then be defined as follows.

Objective	(Secondary) end point	
Metric 1. Time required to compute different queries of interest within the BC registry	Metric definition: Time to have an answer to the 3 queries (BC1, BC2 and BC3) with information from the BC registry - across sites Note 1: should include time of the BC specialist and supporting team (spending most of the time) Note2: should be the same between G1 and G2)	
	 Measurement: TBCx. User entry in dedicated "Data User form" (RedCap) for each of the queries 	
Metric 2: Accuracy of measurement	Metric definition: accuracy of the answer for each of the parameter between AIDAVA and the BC specialist	
	 Measurement: For each of the query (BC1, BC2, BC3), HBCx. Ask the value from the human (through RedCap Form) ABCx: get the value computed by AIDAVA ACCx: accuracy of calculation by AIDAVA (ABCx) compared to BC specialist (HBCx) 	

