9.1 Statistical Hypotheses

The primary objective is to demonstrate that G1 of the AIDAVA prototype is superior to the current situation in achieving data curation and publishing of personal health data; and that G2 is superior to G1. Improved efficiency will be measured through 4 endpoints i.e. M1 (usability of the tool), M2 (decreased time to curated data), M3 (high quality of resulting data), M4 (extraction of structured data from text).

- The 2 critical metrics are M2 (time) and M3 (quality).
- While important, **M1 (usability)** should be possible to improve (more training, increased explanation, ..) and the results of the evaluation will provide directions on how to improve.
- M4 (NLP performance) will improve with the introduction of new technologies (Large Language Models like ChatGPT and BARD) and is therefore less critical for the future of AIDAVA.

Thus, the null hypothesis to be tested in relation to the **primary estimand**¹⁷ is as follows.

• Null hypothesis (H0): The efficiency of data curation and publishing of personal health data is not different between G1 or G2 of the AIDAVA prototype and the current situation. There is no impact due to training on data curation.

vs.

- Alternative hypothesis (H1):
 - G1 of the AIDAVA prototype is more effective than the current situation with respect to the efficiency of data curation and publishing of personal health data and G2 is even more effective than G1.
 - The efficiency improvement is due mainly to the tool; some improvement is related to the training on data curation.

The null and alternative hypotheses corresponding to the secondary estimands are as follows:

Secondary objective for Breast Cancer Use Case:

- Null hypothesis: There is no difference with AIDAVA, to get an answer to specific queries on the BC registry across sites, in terms of accuracy and time.
- Alternative hypothesis (H2-BC): AIDAVA G1 provides correct answers on queries on the BC registries across sites (with an accuracy 90% or higher), while avoiding BC specialists (and supporting team) to spend time. G2 has similar or better results.

¹⁷ estimand (trial objective) is the target of estimation. In AIDAVA, the primary estimand is improved efficiency in data curation

Secondary objective for CVD specialists :

- Null hypothesis: There is no difference to compute SMART score for patients across sites, in terms of accuracy and time with AIDAVA.

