- Alternative hypothesis (H2 CVD): AIDAVA G1 provides an accurate SMART score (accuracy of 80%+) on patients, across sites, without any time spent by CVD specialists. G2 has similar or better results.

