A1	Sum across patient arms for G1 A1.M1 = M1@PDP4 + M1@PDP6 A1.M2.x = M2.x@PDP4 + M2.x@PDP6 A1.M3.x = M3.x@PDP4 + M3.x@PDP6 A1.M4.x = M4.x@PDP4 + M4.x@PDP6	Descriptive Statistics Performance in G1 of the AIDAVA system.			
A2	Sum across patient arms for G2	Descriptive Statistics			

Computed	Description of measures	Test & meaning (per H1)
	A2.M1 = M1@PDP5 + M1@PDP7 A2.M2.x = M2.x@PDP5 + M2.x@PDP7 A2.M3.x = M3.x@PDP5 + M3.x@PDP7 A2.M4.x = M4.1@PDP5 + M4.x@PDP7	Performance in G2 of the AIDAVA system.
A3	Difference in A1 and A2 (i.e. difference between G1 and G2 across all patients)	Unpaired t-test
	Α3.Μ1-Δ = Α1.Μ1 - Α2.Μ1	H1: G2 more usable than G1
	A3.M2.xΔ = A1.M2.x - A2.M2.x A3.M3.x-Δ = A1.M3.x - A2.M3.x	H1: G2 requires less time for curation than G1 H1: G2 enable curation with less human intervention than G1
	A3.M4.X-∆ = A1.M4.x - A2.M4.x	Wilcoxon signed-rank test H1: The NLP system developed in G2 yields a higher precision than the NLP system from G1. H1: The NLP system developed in G2 yields a higher recall than the NLP system from G1.
A4	Difference in P1 and P2 (difference between the 2 patient arms)	Unpaired t-test (effect on training/experience) There is a difference in performance due to training/experience with the system : patients having used G1 are more/not more effective in G2 than patients who work with only one generation of the prototype (G1 or G2)
	Α4.Μ1-Δ = P1.Μ1-Δ - P2.Μ1-Δ	H1: G2 more usable than G1 (due to experience during G1)
	A4.M2.x-Δ = P1.M2.x-Δ - P2.M2.x-Δ A4.M3.x-Δ = P1.M3.x-Δ - P2.M3.x-Δ	H1: G2 requires less time for curation than G1 as patients are more experienced H1: There are less questions of the system unanswered during G2 than in G1 as the patient acquired experience in G1
	A4.M4	Not useful

Secondary Endpoint(s) Analysis

Description of measures	Test & meaning (per H1)
Breast Canc	er
Difference in data points 0 and 1 (i.e. difference between G0 and G1 across a sample of 15 patients) U0.TBCx- Δ = TBCx@SDP0 - TBCx@SDPA U0.EBCx- Δ = EBCx@SDP0 - EBCx@SDP1 U0.ACCx- Δ = ACCx@SDP0 - ACCx@SDP1	Unpaired t-test H1: G2 has more (or same) accuracy than G1 while keeping the same time saving and duration
	Descriptive Statistics around performance in G1 of the AIDAVA system (e.g. mean,)

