Difference in data points 1 and 2 (i.e. difference between G1 and G2 across all patients) U1.TBCx- Δ = TBCx@SDP1 - TBCx@SDP2 U1.EBCx- Δ = EBCx@PSP1 - EBCx@SDP2 U1.ACCx- Δ = ACCx@SDP1 - ACCx@SDP2	Paired t-test H1: G2 has more (or same) accuracy than G1 while keeping the same time saving and duration
Cardiovascu	lar
	Descriptive Statistics around performance in G1 of the AIDAVA system (e.g. mean,)
Difference in data points 1 and 2 (i.e. difference between G1 and G2 across all patients) U1.TCVD- Δ = TCVD@SDP1 - TCVD@SDP2	Paired t-test H1: G2 has more (or same) accuracy than G1 while keeping the same time saving
	Description of measures Breast Canc Difference in data points 0 and 1 (i.e. difference between G0 and G1 across a sample of 15 patients) U0.TBCx- Δ = TBCx@SDP0 - TBCx@SDPA U0.EBCx- Δ = EBCx@SDP0 - EBCx@SDP1 U0.ACCx- Δ = ACCx@SDP0 - ACCx@SDP1 Difference in data points 1 and 2 (i.e. difference between G1 and G2 across all patients) U1.TBCx- Δ = TBCx@SDP1 - TBCx@SDP2 U1.EBCx- Δ = EBCx@PSP1 - EBCx@SDP2 U1.ACCx- Δ = ACCx@SDP1 - ACCx@SDP2 Cardiovascu Difference in data points 1 and 2 (i.e. difference between G1 and G2 across all patients) U1.TCVD- Δ = TCVD@SDP1 - TCVD@SDP2 U1.ACCyD- Δ = ACVD@SDP1 - ACVD@SDP2 U1.ACCyD- Δ = ACVD@SDP1 - ACVD@SDP2

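### No-worse claims for G2 (M3 quality, secondary accuracy and time) are paired with tests of zero difference and no margin, and for M3 they conflict with the superiority objective in Section 9.1

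*Protocol*

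**What the plan says.** Section 9.1 sets the primary objective as showing that G1 beats current practice and that G2 is superior to G1. It lists M3 among the four measures and names M2 and M3 as the critical ones. Its null is that efficiency "is not different between G1 or G2 of the AIDAVA prototype and the current situation".

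Section 9.3 then words the M3 alternative, for both P1 (paired t-test) and P2 (unpaired test), as "H1: G2 provide same or higher quality than G1". The U1 rows, both with a paired t-test, read "H1: G2 has more (or same) accuracy than G1 while keeping the same time saving and duration" for breast cancer and "H1: G2 has more (or same) accuracy than G1 while keeping the same time saving" for CVD. Section 9.1 says of both secondary use cases that "G2 has similar or better results".

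Of the paired t-test, Section 9.3 says: "It is used to determine if there is a significant difference between the two groups". The unpaired test is introduced as "Mann-Whitney U test (unpaired t-test"), so its identity is ambiguous, but either version tests for a difference. No non-inferiority or equivalence margin, shifted null or confidence-limit rule appears. The 90% (breast cancer) and 80% (CVD) accuracy figures in Section 9.1 are absolute targets for G1, not limits on the change from G1 to G2.

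**The concern.** A claim of same or higher is a no-worse claim, so a difference of zero belongs to the alternative. In the test assigned to it, zero is the null. The hypothesis and the test therefore do not answer the same question, and the protocol does not say which result would count as support.

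This matters most for M3. Section 9.2 lists no M3 measure at G0, so G2 against G1 is the only M3 comparison, and what counts as success on a critical metric depends on which section one reads. Under Section 9.1, equal quality is a failure. Under the P1 and P2 rows, it is a success.

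**Working it through.** **1. Sample-size figure.** Section 9.4 assumes that 50 to 80 subjects are sufficient and targets 15 × 3 sites × 2 use cases = 90 patients. The 90 reproduces. The 50 to 80 cannot be reproduced, because no significance level, power, SD or effect size is given. Everything below is therefore an illustration, with two-sided alpha 0.05 assumed and effects in SD units.

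**2. If support means a significant result.** When G2 truly equals G1, a two-sided 5% test is significant in G2's favour 2.5% of the time (0.05 / 2). When it is significant, it shows higher, not same. A one-sided test with its boundary at zero has the same limit.

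**3. If support means a non-significant result.** The relevant figure is the chance of missing a real loss of d SD: miss = P(|T| ≤ t(0.975, df)), where T is noncentral t.

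- Unpaired, n per group: df = 2n − 2, noncentrality d√(n/2). The P2 group sizes are not stated.
- Paired, n pairs: df = n − 1, noncentrality d√n, with d in SDs of the within-patient difference.

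| Contrast | n | d | Noncentrality | Miss |
|---|---|---|---|---|
| P2, unpaired | 15 per group | 0.5 | 1.37 | 74% |
| P2, unpaired | 30 per group | 0.5 | 1.94 | 52% |
| P2, unpaired | 45 per group | 0.5 | 2.37 | 35% |
| Paired (P1 or CVD U1) | 30 pairs | 0.5 | 2.74 | 25% |
| Paired | 34 pairs | 0.5 | 2.92 | 19% |
| Paired | 40 pairs | 0.5 | 3.16 | 13% |
| Paired | 50 pairs | 0.5 | 3.54 | 7% |
| Paired | 50 pairs | 0.3 | 2.12 | 45% |
| Breast cancer U1, by site | 3 | 0.5 | 0.87 | 92% |
| Breast cancer U1, by specialist | 6 | 0.5 | 1.22 | 83% |

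The 6 is the two breast cancer specialist entries per site on the form in Section 10.3.2, times 3 sites. On this reading, the smaller the sample, the easier it is to conclude same.

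**4. What a margin rule could deliver in P1.** Take a margin of 0.5 SD of the G1 score purely as an example, with no true difference and equal SDs. The SD of the paired difference is √(2(1 − r)) in G1 SD units, where r is the within-patient correlation. Power = P(T > t(0.975, n − 1)), with noncentrality 0.5√n / √(2(1 − r)).

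| r | SD of difference | 40 pairs | 60 pairs |
|---|---|---|---|
| 0.5 | 1.00 | noncentrality 3.16, power 87% | noncentrality 3.87, power 97% |
| 0 | 1.41 | noncentrality 2.24, power 59% | noncentrality 2.74, power 77% |

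The documents give no value for r. The two measurements lie 16 to 18 months apart, with a changed tool and data uploaded afresh (Sections 4.1 and 4.4.4), so a low r cannot be excluded.

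**The case against.** The strongest reply is that Section 9.1 governs. The objective there is superiority, a t-test fits it, and the words 'same or' in two M3 rows are loose drafting that can simply be deleted. That stands as one valid repair. It also means that a no-worse design is not the only correct reading of the plan. It does not remove the mismatch, because the text as written has two incompatible success criteria for M3, and for the secondary contrasts Section 9.1 itself uses the no-worse wording.

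A reader might infer that the sponsor will declare G2 the same whenever the test is not significant, so that a worse G2 would often be reported as no worse. The documents do not support this: no such decision rule is stated. The miss rates show what would follow from that reading, not what is planned.

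A reader might also infer that the tests are weak everywhere. That is not so. With 50 pairs in P1, a 0.5-SD loss is missed only 7% of the time. In the CVD contrast, 34 returning patients out of 45 bring the figure to 19%.

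Finally, the note in Section 3.2.1 that breast cancer query time "should be the same between G1 and G2" is an expectation attached to a metric definition. It is not a tested hypothesis and adds little. The study is also a proof of concept whose output is not used for clinical decisions, which bears on severity.

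**Conclusion.** The point holds as a mismatch within the protocol's own text. Section 9.3 fixes both the claim and the test, and the test cannot establish the claim for M3 in P1 and P2 or for the U1 accuracy and time contrasts. For M3 there is a further conflict with the superiority objective in Section 9.1. This is not detail left to an analysis plan.

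The practical size depends on the contrast. It is large for P2 and for the breast cancer contrasts with 3 to 6 units. In the paired patient contrasts it is moderate to small for a 0.5-SD loss, but still 45% at 50 pairs for a 0.3-SD loss. All of these figures rest on an assumed two-sided 5% level and on effects in SD units. I rate it as should-fix: the M3 conclusion is undefined as written, but the repair is a matter of wording and a decision rule.

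**What to change.** Reconcile Sections 9.1 and 9.3 before any G2 data are seen, in one of two ways for M3:

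- (a) Delete 'same or' and test superiority of G2 over G1, in line with Section 9.1.
- (b) Keep the no-worse claim, amend Section 9.1 to match, and conclude it only if the lower limit of the two-sided 95% confidence interval for G2 minus G1 in P1 lies above the negative of a margin. The margin should be in score points and justified by the sponsor. The 0.5 SD above is an illustration with no basis in the documents.

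For the CVD contrasts in U1, apply the same margin-and-interval rule to accuracy (ACVD) and time (TCVD), each with its own margin. Where a larger value is worse, as for time, use the upper limit of G2 minus G1.

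Report P2 for M3, and the breast cancer contrasts TBCx, EBCx and ACCx, with estimates and confidence intervals, and make no claim of sameness from them.

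The cost is revised wording and, for each no-worse claim kept, one agreed margin. No patients or data are added. The downside is that P2 and the breast cancer contrasts can no longer support a conclusion of no change. Under (b), power in P1 depends on the number of returning patients and on the unknown within-patient correlation.
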